9.2.15.1.7 THERASPHERE ADMINISTRATION DOCUMENTATION

Any technical problems or complications related to the delivery of TheraSphere treatment to the patient must be documented in the medical record. The details of any event and its impact on the patient should be documented on an Adverse Event eCRF. Patients in the Treatment group must certify continued eligibility prior to administration of TheraSphere. A new blood draw for labs and pregnancy and an ECOG Performance Status test should be performed within 48 hours of administration.

Using institutional practices, the activity of each vial of TheraSphere will be determined prior to administration. This activity will be used to calculate the actual dose delivered to the liver and lung which will be recorded on the appropriate eCRF.

Calculation of the liver dose (Gy) delivered:

Calculation of the delivered dose per infusion takes into account the activity lost to lung shunting plus activity associated with residual microspheres in the administration system and is provided by the following formula:

$$\text{Dose (Gy)} = \frac{50[\text{Injected Activity (GBq)}][1-F][1-R]}{\text{Mass of Selected Liver Target (kg)}}$$

where F = lung shunt fraction (determined in Section 9.2.14.1.3)
R = residual fraction (1-fraction of microspheres delivered)

Calculation of residual activity fraction for microspheres:

The fraction of microspheres remaining in the device is calculated using the following formula:

$$R = \frac{(W-b')}{(I-b)}$$

where R = residual activity fraction

b = background dose rate prior to source vial measurement

I = measured dose rate of source vial positioned greater than 30 cm from ionization chamber (or other measuring device)

b' = background dose rate prior to waste measurement and W = average dose rate of shielded waste container (containing discarded vial, microcatheter, tubing) positioned with center in same location as I

Calculation of Actual Lung Radiation Exposure:

Calculation of the lung dose (Gy) delivered in each infusion is provided by the following formula:

$$\text{Lung dose (Gy)} = 50 * \text{activity delivered (GBq)} * F$$

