10.2.2.2 SECONDARY STUDY ENDPOINTS

Time-to-progression will be compared between the Treatment and Control groups from time of randomization to radiological progression (including new liver lesions and extra-hepatic lesions) according to RECIST v 1.1 criteria by investigator determination.

Time-to-untreatable-progression will be compared between the Treatment and Control groups from randomization to radiological progression (including new liver lesions and extra-hepatic lesions) according to RECIST v 1.1 criteria by investigator determination. For patients randomized to the Treatment group, any liver lesion still amenable to TheraSphere treatment is not considered to be an untreatable progression. Untreatable progression will be defined as one of the following:

- Intolerance to sorafenib

- Occurrence of specific contraindications to sorafenib
- Assessment of progression in the target lesions or occurrence of new lesions after treatment and, for patients randomized to the treatment group, a maximum of 2 re-treatments with TheraSphere
- Occurrence of specific contraindications to TheraSphere and or appearance of lung/intestinal shunts or anatomical constraints not correctable by radiological procedures for the Treatment group.
- Confirmed extra-hepatic metastases
- Deterioration of liver function (Child Pugh score >B7)
- Clinical progression to ECOG performance status >1. Such deterioration in PS should be observed at two subsequent evaluations at 8 week intervals.

Time to symptomatic progression (TTSP): from the time of randomization to ECOG performance status >1 with or without tumor progression based on RECIST v1.1. Deterioration in performance status is to be confirmed at two subsequent evaluations at 8 week intervals.

Tumor Response according to RECIST v 1.1 criteria based on investigator assessment. At Baseline, target tumors are identified, read and measured for size. At all subsequent follow-up visits, the images (using the same modality) for the same target lesions will be read and measured and compared back to the Baseline images and then categorized according to the following table:

BEST RESPONSE	RECIST v 1.1
	Change in the sum of diameter of target lesions
CR	Disappearance of all target lesions
PR	≥30% decrease in the sum of diameters of target lesions
SD	Neither CR nor PR nor PD

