6.2.2 Windows

For the purpose of statistical analysis, time windows will need defining for presentations that summarize values by visit. The windows for the visits following baseline will be constructed in such a way that the upper limit of the interval falls half way between the two visits (the lower limit of the first post-baseline visit will be Day 2), as shown below. The assignment of data to visit windows will use the relative day defined in Section 6.2.1.1.

Table 3 Analysis Windows for Assessments Performed at Eight Week Intervals

Week	Scheduled Day	Visit Window for Analysis (Days)
Week 8	57	2 – 85
Week 16	113	86 – 141
Week 24	169	142 – 197
...		
End of Study		Latest assessment available*

*Last assessment should be assigned to a Week X based on the visit windows as well as to the end of study evaluation.

If a patient has more than 1 assessment occurring in the same visit window, the data from the assessment closest to the scheduled day will be used. If 2 assessments have the same distance from the scheduled day, the data of the assessment after the scheduled day will be used. Note that the visit windows will not be used for time-to-event endpoints and subject-level tumor response endpoints (i.e. objective response rate and disease control rate).

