6.4.2.5 Time to Symptomatic Progression

Time to symptomatic progression (TTSP) is defined as the time from date of randomization to date of assessment of ECOG performance status >1 with or without tumor progression based on investigator assessment according to RECIST criteria v1.1. The symptomatic progression is confirmed at the first two subsequent evaluations at least 8 and 16 weeks later, respectively. The date of the first ECOG performance status >1 will be used as the event date in the TTSP analysis (assuming ECOG performance status >1 at the first two subsequent evaluations at least 8 and 16 weeks later, respectively). Illustrative examples are provided in Table 7.

Table 7 Examples of Symptomatic Progression

Week X	Week X+8	Week X+16	Week X+24	Week X+32	TTSP Event
ECOG>1	ECOG>1	ECOG>1	ECOG≤1	ECOG≤1	Yes, event at Week X

ECOG>1	ECOG>1	Missing	ECOG>1	ECOG≤1	Yes, event at Week X
ECOG>1	Missing	ECOG>1	ECOG>1	Missing	Yes, event at Week X
ECOG>1	ECOG≤1	ECOG>1	ECOG>1	Missing	No
ECOG>1	No further ECOG assessments				No
ECOG>1	ECOG>1	No further ECOG assessments			No

Week X denotes that week of the first occurrence of ECOG >1

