8.6.2.3 Time to Symptomatic Progression (TTSP)

TTSP rates will be derived from the Kaplan-Meier estimates for each treatment group; 3, 6, 9, and 12 month TTSP rates will be presented, together with 95% CIs. Quartiles will be presented and 95% CIs will be calculated on the quartiles for each treatment group. A log-rank (two-sided) test will be used to compare TTSP between the two treatment groups at a 0.05 significance level. The HR and corresponding 95% CI will be computed from a Cox proportional hazards model. Plots of the Kaplan-Meier curves will be provided for each treatment group. This analysis will be performed on both the mITT and PP populations.

TTSP (Months) = (Date of first ECOG >1/censor – Date of Randomization + 1)/ 30.4375.

The censoring is performed as follows:

- 1) If a patient does not have a post baseline ECOG assessment, then the TTSP will be censored at the randomization date, regardless of whether or not symptomatic progression has been observed.
- 2) If a patient received a subsequent HCC therapy before symptomatic progression or in the absence of symptomatic progression (note that for this scenario a subsequent HCC therapy may occur before the assessment of ECOG>1 or before either confirmation of ECOG>1 at the first two subsequent assessments at least 8 and 16 weeks later, respectively), the TTSP time will be censored at the last valid post baseline ECOG assessment on or before the start date of the subsequent HCC therapy. If the patient has no post-baseline ECOG assessments on or before the start date of the subsequent HCC therapy, the patient will be censored at the randomization date.
- 3) If a patient did not have a symptomatic progression and did not receive subsequent HCC therapy, the TTSP time will be censored at the last post baseline ECOG assessment date or at the randomization date if the patient does not have any post-baseline ECOG assessments.
- 4) If a patient had symptomatic progression immediately after two or more missed visits (note that for this scenario two or more missed visits may occur before the assessment of ECOG>1 or before either confirmation of ECOG>1 at the first two subsequent assessments at least 8 and 16 weeks later), the patient will be censored at the last post baseline ECOG assessment before the missed visits. If the patient has no post-baseline ECOG assessments before the missed visits, the patient will be censored at the randomization date.

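### As written, TTSP is tied to a patient's first-ever ECOG >1, so an unconfirmed first rise turns a later, fully confirmed deterioration into a censored observation

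*SAP*

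**What the plan says.** Protocol 10.2.2.2 defines TTSP as time from randomization to ECOG >1 and adds: "Deterioration in performance status is to be confirmed at two subsequent evaluations at 8 week intervals". It does not limit the event to the first ECOG >1 ever recorded.

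SAP 6.4.2.5 makes the confirmation rule more specific: "The symptomatic progression is confirmed at the first two subsequent evaluations at least 8 and 16 weeks later, respectively". It then fixes the date: "The date of the first ECOG performance status >1 will be used as the event date in the TTSP analysis". The footnote to Table 7 reads "Week X denotes that week of the first occurrence of ECOG >1", and the formula in SAP 8.6.2.3 begins "TTSP (Months) = (Date of first ECOG >1/censor".

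For a patient with no symptomatic progression and no subsequent HCC therapy, censoring rule 3 in SAP 8.6.2.3 applies: "the TTSP time will be censored at the last post baseline ECOG assessment date or at the randomization date" (the latter if there is no post-baseline ECOG).

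SAP 5.2.2 lists changes from the protocol for TTP and tumor response. It lists none for TTSP.

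On assessment times, the schedules in Protocol 3.0 and SAP 6.1 put ECOG at screening and 8-weekly follow-up, and also at the first TheraSphere work-up, the second work-up and re-treatment. The control group's sorafenib column has no ECOG. Protocol 9.2.15.1.7 adds: "A new blood draw for labs and pregnancy and an ECOG Performance Status test should be performed within 48 hours of administration". SAP 6.2.2 states: "Note that the visit windows will not be used for time-to-event endpoints".

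**The concern.** Three places in the SAP use the word first, and none says what happens when the first ECOG >1 is not confirmed. A programmer who follows the text tests one anchor per patient, finds it unconfirmed, and stops. A later deterioration that lasts for months is then recorded as time free of symptomatic progression.

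TTSP is a secondary endpoint with its own log-rank test, hazard ratio and Kaplan-Meier curves. The literal rule removes real events from all of them. It also narrows the protocol's definition without declaring a change. A programmer who supplies the missing restart would produce a different event set from the same data.

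The chance that a stray rise uses up the anchor grows with the number of ECOG assessments, and the TheraSphere arm has more of them. Whether the loss differs by arm is therefore a fair question, checked below.

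**Working it through.** **1. Table 7 under two rules.** Rule A tests only the first-ever ECOG >1. Rule B tests each ECOG >1 in turn until one is confirmed. Confirmation needs ECOG >1 at the first evaluation at least 8 weeks after the anchor and at the next one at least 16 weeks after it, skipping missing visits.

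| Pattern (Weeks X to X+32) | Table 7 | Rule A | Rule B |
|---|---|---|---|
| >1, >1, >1, ≤1, ≤1 | Yes, X | Yes, X | Yes, X |
| >1, >1, missing, >1, ≤1 | Yes, X | Yes, X | Yes, X |
| >1, missing, >1, >1, missing | Yes, X | Yes, X | Yes, X |
| >1, ≤1, >1, >1, missing | No | No | No |
| >1, then nothing | No | No | No |
| >1, >1, then nothing | No | No | No |
| >1, ≤1, >1, >1, >1 | not in table | **No** | **Yes, X+16** |

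All six rows reproduce under both rules. Row 4 is No either way, because its later run has only two observed values. The deciding pattern is absent, so the sentence, footnote and formula decide, and all three say first.

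**2. One patient.** ECOG 2 at Week 8, 1 at Week 16, and 2 or worse at Weeks 24, 32, 40 and 48; no subsequent HCC therapy. The visit day is 7 × week + 1 (as in SAP Table 3), and TTSP in months is day/30.4375.

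- Rule A: the Week 8 anchor fails at Week 16, so the patient is censored at Week 48: 337/30.4375 = 11.07 months.
- Rule B: event at Week 24, confirmed at Weeks 32 and 40: 169/30.4375 = 5.55 months.
- Hybrid (accept any confirmed run but keep the date of the first ECOG >1): event at Week 8: 57/30.4375 = 1.87 months.

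**3. Chance of losing a run first seen at Week 32.** Let p be the chance of a transient ECOG >1 at one assessment. The documents do not give p, so a range is shown. A rise at Week 24 is confirmed by Weeks 32 and 40 and is not lost (the event is dated 8 weeks early). The assessments that can lose the run are Weeks 8 and 16 in control (m = 2), plus an assumed Week 3 look for unilobar TheraSphere (m = 3), plus an assumed Week 7 look for bilobar (m = 4). The loss is about 1 − (1 − p)^m:

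| p | Control, m = 2 | Unilobar, m = 3 | Bilobar, m = 4 |
|---|---|---|---|
| 1% | 2.0% | 3.0% | 3.9% |
| 5% | 1 − 0.95² = 9.8% | 1 − 0.95³ = 14.3% | 1 − 0.95⁴ = 18.5% |
| 10% | 19.0% | 27.1% | 34.4% |

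Full enumeration, allowing two stray rises to confirm each other, gives 9.5%, 14.0% and 18.3% at p = 5%.

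**4. Effect on the comparison with no true difference.** Simulation with 15,000 patients per arm and the same p at every look. Assumed: median 35 weeks to sustained ECOG >1; median survival 30 weeks after that; a competing hazard of earlier death; extra TheraSphere looks at Week 3 (unilobar), Weeks 3 and 7 (bilobar), or Weeks 3, 7, 29 and 45 (bilobar with two re-treatments). The Monte Carlo SE of the HR is about 0.02.

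| p | Events lost, control | Events lost, TheraSphere | HR, Rule A | HR, Rule B |
|---|---|---|---|---|
| 1% | 2.9–3.2% | 3.4–4.8% | 0.98–1.00 | 1.01–1.02 |
| 2% | 4.9–6.4% | 6.9–9.1% | 0.94–1.00 | 0.99–1.02 |
| 5% | 13.0–13.5% | 16.0–19.7% | 0.93–0.95 | 0.99–1.03 |
| 10% | 22.1–22.5% | 25.7–32.4% | 0.88–0.97 | 0.99–1.03 |

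A separate simulation with other survival assumptions (8,000 per arm, SE of log HR about 0.026) gave a Rule A HR of 1.03 with 3% at every look. With 3% at routine visits and 10% at the TheraSphere-only looks it was 0.91, or 0.96 if no rise can occur at Week 3.

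**The case against.** The strongest reply is that the event-date sentence only means the event is dated at onset and not at confirmation. It carries on with the condition that the two later evaluations also show ECOG >1, Table 7 is offered as illustration, and the protocol has no first-ever limit. That may well be the intent. It does not remove the problem, because the footnote and formula repeat the first-occurrence wording and no restart is stated.

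A reader might infer that Table 7 row 4 proves the restrictive rule. It does not: it is No under either rule.

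A reader might also infer that the rule biases TTSP toward TheraSphere. The documents do not support that:

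- They give no rate of transient ECOG >1. The 57% and 61% in Protocol 5.3 are fatigue rates from cited series. Only the 61% is called transient, and it concerns the week after administration.
- Protocol 9.2.15.1.7 places the extra ECOG beside the requirement to certify continued eligibility before dosing, and eligibility requires ECOG ≤1. A rise may therefore be less likely there than at routine visits.
- Follow-up visits have a ±14-day window, so one assessment could serve as both the second work-up look and the Week 8 visit.
- An extra look can act the other way. A Week 3 rise is checked at Weeks 16 and 24, so a normal Week 8 is skipped. With ECOG >1 from Week 16 on, the event is dated Week 3 (22/30.4375 = 0.72 months) where a control patient with the same 8-weekly values is dated Week 16 (113/30.4375 = 3.71 months).
- Under SAP 8.6.2, TTSP is tested only if OS and each endpoint ahead of it are significant. A raised rejection rate for TTSP alone is not a study-wise error rate.

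These points stand. They limit the between-arm claim, but not the loss of events.

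**Conclusion.** The point holds as a defect in the written rule. Followed literally, SAP 6.4.2.5 and 8.6.2.3 score a pattern of >1, ≤1, >1, >1, >1 as censored, although its last three values meet the protocol definition. This needs only the text and the absence of subsequent HCC therapy; if such therapy starts before the run is confirmed, rule 2 governs the censoring.

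Real events are lost in both arms. Under the simulation assumptions the share is about 3–5% at a transient rate of 1% per look and 13–20% at 5%. The loss may be larger in the TheraSphere arm, which has about one extra ECOG look if unilobar, two if bilobar, and up to four with two re-treatments. The effect on the hazard ratio is negligible near 1% and roughly 0.9 only under higher assumed rates. Its size and direction in this trial cannot be fixed from the documents, and a bias toward TheraSphere should not be claimed.

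**What to change.** In SAP 6.4.2.5 and 8.6.2.3, define the TTSP event as the earliest ECOG >1 assessment that is itself followed by ECOG >1 at the first two subsequent evaluations at least 8 and 16 weeks later, and date it at that assessment. State that an unconfirmed ECOG >1 does not end the search. Change the formula to use that date, reword the Table 7 footnote so that Week X need not be the only candidate anchor, and add the row >1, ≤1, >1, >1, >1 = Yes, event at Week X+16.

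If the first-ever restriction is intended, say so and list it in SAP 5.2.2 as a change from the protocol.

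Optionally, add a sensitivity analysis in which only the 8-weekly visits common to both arms can start a run. It addresses the unequal looks and the Week 3 backdating, which the restart does not remove. It should not replace the main analysis, because it sets aside valid ECOG data and the protocol contains no such limit.

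The cost is a few lines of SAP text, one table row and a small programming change. No new data are needed.

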6.4.3 Additional Efficacy Variables

6.4.3.1 TTP according to mRECIST criteria by blinded central image review

TTP by blinded central review is defined as the time from date of randomization until date of radiological progression by the blinded central image review, according to mRECIST.

6.4.3.2 Disease control rate (DCR) according to RECIST v1.1 criteria by investigator determination

DCR by investigator assessment is defined as the proportion of randomized patients achieving a best overall response of CR, PR, or SD as defined by RECIST v 1.1, as determined by the investigator.

If a patient received subsequent HCC therapy, imaging assessments after the start date of the subsequent HCC therapy will be excluded from the calculation of best overall response and DCR. Patients who do not have any post baseline tumor assessments for any reason on or prior to the start date of the subsequent HCC therapy, are considered non-responders and are included in the denominator when calculating the DCR.

6.4.3.3 ORR according to mRECIST criteria by blinded central image review

ORR by blinded central review is defined as the proportion of randomized patients achieving a best overall response of CR or PR, as defined by mRECIST, as determined by blinded central image review.

If a patient received subsequent HCC therapy, imaging assessments after the start date of the subsequent HCC therapy will be excluded from the calculation of best overall response and ORR. Patients who do not have any post baseline tumor assessments for any reason on or prior to the start date of the subsequent HCC therapy, are considered non-responders and are included in the denominator when calculating the ORR.

6.4.3.4 DCR according to mRECIST criteria by blinded central image review

DCR by blinded central review is defined as the proportion of randomized patients achieving a best overall response of CR, PR or SD, as defined by mRECIST, as determined by blinded central image review.

If a patient received subsequent HCC therapy, imaging assessments after the start date of the subsequent HCC therapy will be excluded from the calculation of best overall response and DCR. Patients who do not have any post baseline tumor assessments for any reason on or prior to the start date of the subsequent HCC therapy, are considered non-responders and are included in the denominator when calculating the DCR.

6.4.3.5 PFS according to RECIST v1.1 criteria by investigator assessment

PFS by investigator assessment is defined as the time from date of randomization until date of progression determined by the investigator, according to RECIST v1.1, or death due to any cause, whichever occurs first.

6.4.3.6 PFS according to mRECIST criteria by blinded central image review

PFS by blinded central image review is defined as the time from date of randomization until date of progression determined by the blinded central image review, according to mRECIST, or death due to any cause, whichever occurs first.

6.4.3.7 Duration of objective response

The duration of objective response will be determined for patients who have a best overall response of CR or PR. Duration of objective response is defined as the time from first date of overall response of CR or PR until date of PD, or death due to any cause, whichever occurs first. If a patient did not die or progress then the date of the last radiological assessment will be used in the calculation.

Duration of objective response will be assessed separately by investigator assessment by RECIST 1.1 and by blinded central image review by mRECIST.

6.4.3.8 Duration of Disease Control

The duration of disease control will be determined for patients who have a best overall response of CR, PR or SD. Duration of disease control is defined as the time from first date of overall response of CR, PR or SD until date of PD, or death due to any cause, whichever occurs first.

Duration of disease control will be assessed separately by investigator assessment by RECIST 1.1 and by blinded central image review by mRECIST.

6.4.3.9 *Depth of response (DoR)*

DoR is defined as the percentage change from baseline to nadir in the sum of the longest diameters of target lesions. If a patient received a subsequent HCC therapy, tumor assessments after the start date of the subsequent HCC therapy will be excluded from the calculation of DoR.

DoR will be assessed by investigator assessment by RECIST 1.1, and also by blinded central image review by mRECIST. In addition, DoR will be assessed for the following subgroups based on tumor replacement (%) at baseline:

- >10% tumor replacement by blinded central review
- >20% tumor replacement by blinded central review

6.4.3.10 *Post-Treatment Tumor Shrinkage (PTTS)*

PTTS is defined as the proportion of randomized patients achieving a $\geq 20\%$ decrease in the sum of the longest diameters of target lesions, separately at the Week 8, 16, and 24 analysis visits (as defined in Table 3). PTTS will be assessed separately by investigator assessment by RECIST 1.1 and by blinded central image review by mRECIST.

If a patient received a subsequent HCC therapy, tumor assessments obtained after the start date of the subsequent HCC therapy will be excluded from the determination of achieving the threshold of PTTS at each analysis visit. Patients without post baseline tumor assessments on or prior to the start date of the subsequent HCC therapy are considered non-responders and are included in the denominator when calculating the PTTS.

6.4.3.11 *Tumor Marker for HCC (Alpha Fetoprotein, AFP)*

AFP will be collected along with laboratory data and will be presented similarly. Change from baseline will be calculated.

AFP response, defined as a $\geq 50\%$ decrease in AFP levels for patients with a baseline AFP level of ≥ 200 ng/mL, will also be calculated. The following additional definitions of AFP response will also be calculated:

- a $\geq 50\%$ decrease in AFP levels for patients with a baseline AFP level of ≥ 400 ng/mL
- a $\geq 20\%$ decrease in AFP levels for patients with a baseline AFP level of ≥ 20 ng/mL

For each definition, the AFP response is derived per patient, and the percentage of patients achieving an AFP response is calculated based on the number of patients meeting the condition of the baseline AFP level in the definition. If a patient received a

subsequent HCC therapy, AFP assessments obtained after the start date of the subsequent HCC therapy will be excluded from the determination of AFP responses.

